11.3.3. Efficacy Analysis Population

The efficacy analysis population will include all enrolled patients who receive any amount of andexanet treatment, undergo surgery, and have a baseline anti-fXa activity analyzed by central laboratory at or above the evaluability threshold (75 ng/mL for apixaban, edoxaban and rivaroxaban, and 0.25 IU/mL for enoxaparin). The primary, secondary, and exploratory efficacy endpoint will be analyzed based on the efficacy analysis population.

11.4. Baseline and Demographic Characteristics

Baseline and demographic characteristics will be summarized for all populations listed above. Data will be summarized using descriptive statistics of frequencies for categorical data and means, medians, standard deviations, minimums, and maximums for continuous data. No inferential analyses of these data are planned.

11.5. Efficacy Endpoints and Analyses

Analysis of primary, secondary, and exploratory efficacy endpoints will be based on the Efficacy Analysis Population.

11.5.1. Definitions

Hemostasis will be assessed from the start of surgery to the end of the procedure. Categories for the assessment of intraoperative hemostasis are provided in Table 3.

Table 3: Intraoperative Hemostasis Categories

Category	Definition
Excellent	Normal hemostasis during the procedure
Good	Mildly abnormal hemostasis as judged by quantity or quality of blood loss (e.g., slight oozing from surgical wounds)
Moderate	Moderate abnormality in intraprocedural hemostasis (e.g., controllable bleeding) but no need for additional systemic procoagulant products *
Poor	Severe hemostatic abnormality during the procedure (e.g., severe refractory hemorrhage) and need for additional systemic procoagulant products *

* Tranexamic acid excluded.

The evaluation period for anti-fXa activity covers the period of time from 5 minutes following the end of the andexanet bolus to just prior to the end of the andexanet infusion. The baseline measurement will be the last value obtained prior to andexanet treatment.

The hemostasis evaluation would exclude unexpected blood loss due to surgical complications that may cause uncontrolled bleeding, such as unintended injury of a major vessel or parenchymal tissue.

11.5.2. Efficacy Endpoints

11.5.2.1. *Primary Efficacy Endpoint*

The primary efficacy endpoint is the achievement of effective hemostasis, as determined by the surgeon's assessment of intraoperative hemostasis and confirmed by adjudication by an independent EAC (see Table 3).

For each patient, hemostasis will be considered to be effective if the intraoperative hemostasis category is Excellent or Good, and ineffective if the intraoperative hemostasis category is Moderate or Poor.

A patient will be deemed non-evaluable if s/he meets the criteria specified in the EAC Charter.

11.5.2.2. Secondary Efficacy Endpoint

The secondary efficacy endpoint is the percent change in anti-fXa activity from baseline to the evaluation period nadir. The evaluation period starts 5 minutes after the end of the andexanet bolus and ends just prior to the end of the andexanet infusion.

Patients who do not have at least 1 anti-fXa activity level within the evaluation period will have percent decrease imputed as 0.0% (i.e., using the baseline value as the nadir value).

11.5.2.3. Exploratory Efficacy Endpoints

The following efficacy endpoints will be analyzed as exploratory:

- Relationship between intraoperative hemostasis and anti-fXa activity.
- Anti-fXa activity as measured by additional parameters, including, but not limited to: on-treatment nadir, absolute change from baseline to on-treatment nadir, number of patients with percent reduction from baseline > 80%.
- Reversal of anticoagulant effect as measured by TG parameters (with ETP as the primary measure).
- Occurrence of receiving 1 or more RBC transfusions from start of the andexanet bolus through 12 hours after the end of surgery.
- The number of RBC units transfused per patient from the start of the andexanet bolus through 12 hours after the end of surgery.
- The use of non-RBC, non-platelet blood products and/or hemostatic agents (both systemic and topical) through 12 hours after the end of surgery.
- Observed amount of intraoperative blood loss.
- Difference between observed blood loss and predicted blood loss.
- Transfusion-corrected change in hemoglobin from baseline to nadir within 12 hours after the end of surgery.
- Time from the signing of informed consent to the start of surgery.
- Time from clinical presentation at treatment facility to the start of surgery.
- Length of index hospitalization, assessed at the Day 30 visit.
- Time hospitalized in a PACU, assessed at the Day 30 visit.
- Time hospitalized in an ICU, assessed at the Day 30 visit.
- Length of surgery.
- Total time in OR.
- Occurrence of re-hospitalization, within 30 days of enrollment, including length of re-hospitalization (through 30 days post enrollment).

- Occurrence of post-surgical major bleeding, as defined by ISTH criteria (see Section 4.1), within 12 hours after the end of the initial surgery.
- Occurrence of re-operations for bleeding, including for surgical wound hematomas, within 12 hours after the end of the initial surgery.
- Change from baseline in TFPI activity post-administration of andexanet.
- Change from baseline in anti-IIa activity (only patients taking enoxaparin).

11.5.3. Statistical Methodology for Endpoint Analyses

All efficacy analyses will be performed on the efficacy analysis population.

The primary endpoint, the proportion of patients who have effective hemostasis, will be summarized with a 95% CI.

The secondary endpoint, percent change in anti-fXa activity from baseline to the nadir for the evaluation period, will be assessed with a 2-sided 95% nonparametric CI for the median.

For the exploratory endpoints, counts data will be summarized by observed rates and associated 95% CIs. Continuous endpoints will be summarized by means or medians and associated 95% CIs.

11.6. Determination of Sample Size

Approximately 100 patients will be enrolled. After accounting for 20% attrition (e.g., canceled surgeries, discontinued and/or non-evaluable patients, or baseline anti-fXa activity analyzed by central laboratory less than the evaluability threshold), a sample size of 80 patients will provide an estimate of the proportion of achieving effective (excellent or good) hemostasis with a margin of error (half width of the 95% confidence interval) that is less than 11%.

11.7. Safety Endpoints and Summaries

Safety will be assessed by examining the following endpoints and analyzed in the Safety Analysis Population:

- AEs (including SAEs), vital signs, physical examinations, and clinical laboratory measurements.
- TEs within 30 days of enrollment, including those suspected and confirmed by adjudication.
- Centrally-adjudicated deaths within 30 days of enrollment, including all-cause mortality and cardiovascular mortality.
- Antibodies to FX, FXa, andexanet, and HCPs.

11.7.1. Adverse Events

Treatment-emergent adverse events, including preferred terms defined by the Medical Dictionary for Regulatory Activities (MedDRA), will be summarized by system organ class. Arterial and venous thromboembolic events, considered AESIs, will be summarized separately.

The number of events, the number of patients, and the percentage of patients who experienced at least 1 TEAE will be presented. The TEAEs that are considered by the Investigator to be related to the andexanet, TEAEs that lead to early withdrawals, and serious TEAEs will be summarized in the same manner. Frequent TEAEs will also be summarized.

All potential post-surgical bleeding events will be assessed by the EAC and summarized descriptively, including whether patients were re-anticoagulated prior to the event. Postoperative major bleeding events will be additionally adjudicated by the EAC.

Concomitant medications will be coded using the World Health Organization (WHO) Drug Dictionary.

11.7.2. Thrombotic Events

All TEs will be assessed by the EAC and summarized descriptively, including whether patients were re-anticoagulated prior to the event.

11.7.3. Deaths

All deaths will be assessed by the EAC. Deaths due to cardiovascular causes (i.e., resulting from MI, sudden cardiac death, heart failure, stroke, cardiovascular procedures, cardiovascular hemorrhage, and other cardiovascular causes) will be classified as related to bleeding or non-hemorrhagic.

11.7.4. Laboratory Parameters

Clinical laboratory parameters performed at the Central Laboratory (e.g., anti-fXa activity and TG) will be summarized by time point. For patients with anti-fXa activity levels obtained by a local laboratory assay for purposes of eligibility (for patients with a time from last dose greater than 15 hours), values will be documented but not formally analyzed.

Baseline values, the values at each subsequent visit, and changes from baseline will be summarized for each of the quantitative laboratory assessments.

11.7.5. Vital Signs

Vital signs will be summarized using actual values and change from baseline at pre-specified time points for each treatment group. Descriptive statistics, including threshold-based outlier analyses, will be presented.

11.7.6. Physical Examinations

Findings on physical examination will be summarized in a listing.

11.7.7. Antibodies

The presence of antibodies (anti-andexanet, anti-fX, anti-fXa, anti-HCPs, and/or nAb activity) will be summarized in a listing.

11.8. Interim Analyses

No interim efficacy analyses are planned for this Phase 2 study. During the conduct of the study, interim monitoring of safety data by the DSMB will commence after 50 patients are enrolled, then performed periodically at a frequency of approximately every 6 months.

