---------------------	--

	
samples will be taken at baseline and Day 30 to assess immunogenicity against andexanet, FX, FXa, neutralizing antibodies, and HCPs. The Day 30 visit may be conducted by phone if necessary to minimize nonessential visits.
 
The independent EAC will adjudicate all deaths, TEs, post-surgical bleeding events (e.g., surgical hematomas), and hemostatic efficacy. The independent EAC will be blinded to all anti-fXa levels.
 
An independent Data Safety Monitoring Board (DSMB) will review all safety data approximately every 6 months and will be empowered to recommend modifying or stopping the trial for safety reasons if warranted. All AEs, including SAEs, and survival will be followed through the Day 30 post-treatment visit. In addition, patients who experience an andexanet-related AE or SAE will be followed until the AE or SAE is resolved or until a new stable baseline is established, even if this occurs after the Follow-up Day 30 visit.

Study Periods	
The study duration for any individual patient will be up to 37 days. There are 4 study periods. Study periods are defined as follows:
 
 • Screening Period: Day 1. • Pre-surgical Assessment Period: Day 1. • Treatment Period: Day 1. 
 ◦ Additional dosing during extended surgeries beyond initial andexanet dosing regimen (~2.5 hours) but no greater than a total 6.5 hours (including both the initial regimen and the extended infusion). ◦ Re-dosing (low dose bolus and infusion) may occur within 12 hours after completion of the first course of andexanet treatment (but after the conclusion of the surgical procedure) if protocol specified criteria are met, at the investigator's discretion. • Safety Follow-up Period: Days 1–30 + 7.

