The primary efficacy endpoint is the achievement of hemostatic efficacy, as determined by the surgeon’s assessment of intraoperative hemostasis using a pre-specified 4-point scale (Section 11.5.1) and confirmed by adjudication by an independent Endpoint Adjudication Committee (EAC).

In addition to hemostatic efficacy, the EAC will adjudicate all deaths, TEs, and post-surgical major bleeding events (e.g., surgical hematomas). The EAC will be blinded to all anti-fXa levels. An independent Data Safety Monitoring Board (DSMB) will review all safety data approximately every 6 months.

In addition to the efficacy and safety objectives and endpoints, information obtained from this study is expected to include dosing considerations (adequacy of dosing and duration of dosing required) that will be used to inform a subsequent randomized Phase 3 trial for registrational purposes.

All AEs, including SAEs, and survival will be followed through the Day 30 post-treatment visit. The study schedule of activities can be found in [Appendix A](#).

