Sponsor. Thrombotic events, both suspected and confirmed by adjudication, will be tracked as safety endpoints for the study. To mitigate the risk of TEs, Investigators are encouraged to consider resumption of an anti-thrombotic agent (preferably oral) as soon as it is clinically appropriate. Additional clinical precautions to mitigate thrombotic risk in postoperative care such as early mobilization, sequential compression devices or other routine measures should also be strongly considered.

Prior and ongoing clinical studies have identified infusion reactions of mild or moderate intensity as an AE related to administration of andexanet (described in Section 1.4.5). Patients in this study will receive andexanet in an inpatient, monitored setting under medical supervision and immediate access to resuscitative measures. Infusion reactions observed in prior and ongoing studies have had their onset during the infusion itself.

Whether or not patients have been discharged from the hospital, they will undergo the Study Day 2, Study Day 3, and Follow-up Day 30 visits to assess safety. Due to the theoretical possibility of antibody formation to andexanet, FX, FXa, or HCPs, antibody testing will be performed at baseline and at the Study Day 30 visit (see Section 3.7 for modifications due to COVID-19 guidelines).

The independent EAC, in addition to adjudicating the primary endpoint, will also adjudicate all TEs, deaths, and all post-surgical bleeding events using pre-defined criteria as described in their charter. A DSMB will review all safety data approximately every 6 months and will be empowered to recommend modifying or stopping the trial for safety reasons if warranted. In addition, safety data will be reviewed by the Sponsor at an ongoing basis. Guidelines for the management of specific AEs and intraoperative rescue strategies are provided in Section 8.0.

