Importantly, given the level of uncertainty with this risk, we believe it will be prudent to monitor the frequency of TEs on an ongoing basis as the study progresses. Investigators will be issued guidance discussing COVID-19 and its putative pro-thrombotic effect. Within this guidance, Investigators will be asked to maintain vigilance for potential TEs and to promptly report them should they be clinically suspected. Fortunately, monitoring is already in place, as TEs are designated as AESIs in the protocol, and the DSMB is tasked with evaluating safety data on a continuing basis. Within the protocol, Investigators are asked to monitor for TEs and submit them for adjudication when they occur. Furthermore, Investigators are encouraged to reinitiate anticoagulation as soon as medically warranted to prevent thrombosis.

Finally, as FDA and EMA COVID-19 guidelines encourage reducing nonessential study visits, the Day 30 visit may be conducted by phone, and the sample collection for nAb evaluations at Day 30 are optional. Additional laboratory sampling indicated for the Day 30 visit ([Appendix A](#)) may be conducted at follow-up visits per the standard of care to minimize nonessential study visits.

In summary, early reports have suggested that COVID-19 infection may be associated with a pro-thrombotic state. Measures have been implemented to monitor for TEs in the study.

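### Section 11.8 holds back the first DSMB safety review until 50 of about 100 patients are enrolled, which conflicts with the continuing review relied on in Section 3.7 and, unless accrual is fast, with the 6-monthly review promised elsewhere

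*Protocol*

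**What the plan says.** All references are to the Amendment 2 body of the Protocol. The Amendment 1 body bound into the same file leaves the DSMB schedule to the charter; it is superseded and is not used here.

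- **Section 11.8:** there are no interim efficacy analyses; "interim monitoring of safety data by the DSMB will commence after 50 patients are enrolled", with later reviews at intervals of about 6 months.
- **Section 11.6:** "Approximately 100 patients will be enrolled".
- **Section 3.1:** "An independent Data Safety Monitoring Board (DSMB) will review all safety data approximately every 6 months". No start condition is given.
- **Section 3.5:** "A DSMB will review all safety data approximately every 6 months and will be empowered to recommend modifying or stopping the trial for safety reasons". Again there is no start condition. The synopsis (Study Design) says the same.
- **Section 3.7**, on thrombotic risk during the pandemic: monitoring is described as existing already, partly because "the DSMB is tasked with evaluating safety data on a continuing basis".
- **Section 3.6** counts independent DSMB reviews among the reasons for calling the safety plan robust, and concludes that the risks to patients are justifiable.

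**The concern.** The sections that describe patient protection (synopsis, 3.1, 3.5, 3.6, 3.7) read as if the DSMB is active from the start. The section that sets its timetable does not activate it until 50 patients are in. A site or ethics committee reading 3.5 to 3.7 would expect a safeguard that 11.8 postpones.

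The delay matters because of the setting. Section 1.1 says andexanet has not been evaluated in patients needing urgent surgery. Section 3.5 treats thrombotic events as a realistic prospect. Section 3.6 notes that reversing anticoagulation and surgery each raise thromboembolic risk. The synopsis and Section 3.5 give the DSMB, and no other body, the power to recommend modifying or stopping the trial on safety grounds. Section 11.8 leaves that power without a scheduled occasion for use during the first half of enrolment.

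**Working it through.** **1. The plan's own figures.** Section 11.6 takes 100 enrolled less 20% attrition: 100 × (1 − 0.20) = 80 evaluable. The worst-case 95% half-width at n = 80 is 1.96 × √(0.5 × 0.5 / 80) = 10.96%, which reproduces the stated bound of under 11%. The target of about 100 is therefore internally consistent and is the right denominator.

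**2. Share of enrolment before the first review.** 50 / 100 = 50%.

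**3. Section 11.8 against Section 3.7.** One section has DSMB monitoring beginning at 50 enrolled; the other has it continuing and already present. No accrual rate makes both true for the first 50 patients.

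**4. Section 11.8 against the 6-monthly statements.** Section 11.8 keeps the interval and adds a start condition. The two agree only if 50 patients accrue within about 6 months: 50 / 6 = 8.3 patients per month. The Protocol states no accrual rate, so the rates below are assumptions.

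| Assumed accrual (patients/month) | Months to 50 patients | 6-monthly dates passed before DSMB review starts |
|---|---|---|
| 2 | 50/2 = 25 | 4 |
| 4 | 50/4 = 12.5 | 2 |
| 5 | 50/5 = 10 | 1 |
| 10 | 50/10 = 5 | 0 |

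**5. What could accrue first (illustration only).** Expected thrombotic events = 50 × rate, assuming all 50 are treated and followed for 30 days. The rates are assumptions:

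- 5%: 50 × 0.05 = 2.5 events
- 15%: 50 × 0.15 = 7.5 events

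**6. What operates before 50 patients.** The independent Endpoint Adjudication Committee (EAC) adjudicates deaths, thrombotic events and post-surgical bleeding (Sections 3.1, 12.0). Serious events and thrombotic events go to the sponsor within 24 hours (Sections 9.1.3, 9.2.1). The sponsor reviews safety data on an ongoing basis (Section 3.5). Section 12.0 gives the EAC adjudication only, and sponsor review is not independent. The Protocol text shown provides no earlier DSMB look, event-triggered review or stopping threshold.

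**The case against.** The strongest reply is that 11.8 adds detail and contradicts nothing. The other sections give a frequency and no first date, and with fast accrual the statements coincide. The Amendment 2 change list records that DSMB timing was clarified in the same amendment that cut the sample from 200 to 100, so the start rule may be deliberate. This stands in part: the clash with the 6-monthly wording is conditional on accrual. It does not answer Section 3.7.

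A reader might infer that half the trial runs without independent oversight. The documents do not support that. The EAC is independent and works throughout. The DSMB reviews all safety data, so the first 50 patients are reviewed late and are not left out. What is absent is scheduled DSMB review. Nor does it follow that the board could protect few patients, since about 50 remain to be enrolled at the trigger.

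A reader might also carry over the ANNEXA-4 rates in Section 1.4.7 and expect about 5 thrombotic events (50 × 34/352 = 4.8) and 8 deaths (50 × 54/352 = 7.7) before the first look. Those patients had acute major bleeding, 64% of it intracranial. Section 4.2 of this trial excludes acute life-threatening and intracranial bleeding, recent thrombotic events, sepsis and shock. Section 3.4.2.1 cites 2.3% mortality for urgent surgery, which would give 50 × 0.023 = 1.2 deaths. That cohort is a general surgical one and may understate risk here, but the spread shows that neither count is a dependable forecast. In a single-arm trial with high background thrombotic risk, event counts also do not measure preventable harm.

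Finally, Section 12.0 leaves committee activities to charters, which are not shown. The DSMB charter may provide an earlier or ad hoc review. If so, 11.8 misstates the arrangement and still needs correcting.

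**Conclusion.** The point holds as an inconsistency with a practical safety consequence. Followed as written, Section 11.8 schedules no DSMB review for the first 50 of about 100 patients, in a surgical setting where the drug had not been studied. The conflict with Section 3.7 is direct. The conflict with the synopsis and Sections 3.1 and 3.5 arises if accrual is slower than about 8.3 patients per month; at assumed rates of 2 to 5 per month, one to four review dates would pass. Other safety processes continue, but none has the DSMB's independent mandate to recommend modifying or stopping the trial.

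The size is 50% of planned enrolment and, for an assumed 30-day rate of 5% to 15%, about 2.5 to 7.5 thrombotic events among the first 50 treated patients. The event range is illustrative and does not predict what this trial will see.

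**What to change.** Amend Section 11.8 so that the first DSMB safety review takes place at the earlier of:

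- about 6 months after the first patient is dosed; or
- a patient count agreed with the DSMB and well below 50.

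Reviews then continue about every 6 months. A count of 25 treated patients is one example; nothing in the documents singles it out, and the board should settle the number. Make the synopsis, Sections 3.1, 3.5 and 3.7, and the DSMB charter state the same schedule. Section 3.7 should describe DSMB review as periodic unless continuing review is really intended.

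The cost is one or a few additional meetings of an existing board, depending on accrual, plus a protocol amendment with the ethics approval that Sections 13.1 and 13.6 require. No efficacy look is added, so the planned efficacy estimates and their confidence intervals are unaffected.

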11.9. Subgroup Analyses

Consistency of efficacy across important subgroups will be investigated within each cohort. At a minimum, primary efficacy will be summarized for subgroups of sex (male, female), race (any race with at least 5 members, all others combined), age (< 65 years, \geq 65 years, \geq 75 years), anticoagulant, baseline anti-fXa activity categories (e.g., above and below thresholds of 30 ng/mL, 50 ng/mL, 75 ng/mL), procedure type (e.g., orthopedic, abdominal, thoracic, neurosurgical), duration of surgery (\leq 2 hours, 2-4 hours, $>$ 4 hours), and volume of blood loss (above and below the median). Other subgroup analysis may be considered based on the actual enrollment. Further detail of the subgroup analysis will be described in the Statistical Analysis Plan.

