10.4.2. Intraoperative Blood Loss

Investigators will report predicted blood loss and observed blood loss during surgery for each patient. Predicted blood loss must be determined by the investigator prior to the first incision. Observed blood loss will be reported as an estimate of blood loss in milliliters at the end of surgery. It is an intraoperative assessment and will not be updated for post-closure blood loss. Observed blood loss will be measured against predicted blood loss.

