12.0 STUDY COMMITTEES AND COMMUNICATIONS

Each of planned study committees will have a charter outlining its activities and responsibilities. In brief, the purpose of each committee is as follows:

- **Independent EAC:** Adjudication of hemostatic efficacy, deaths, TEs, and post-surgical bleeding events for all patients. The EAC will be blinded to all anti-fXa levels.
- **Independent DSMB:** Monitor all safety data and make recommendations for study modification or stopping due to safety reasons.

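### The baseline anti-fXa cut points in Section 11.9 leave the lower group empty for direct inhibitors, and the split on blood loss cannot test consistency of efficacy

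*Protocol*

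**What the plan says.** Section 11.9 sets a minimum list: "At a minimum, primary efficacy will be summarized for subgroups of sex (male, female") and further factors, among them "baseline anti-fXa activity categories (e.g., above and below thresholds of 30 ng/mL, 50 ng/mL, 75 ng/mL") and "volume of blood loss (above and below the median"). It names no analysis population of its own and leaves further detail to the SAP, which is not at hand.

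Under Section 11.3.3, patients in the Efficacy Analysis Population must have received andexanet, undergone surgery and "have a baseline anti-fXa activity analyzed by central laboratory at or above the evaluability threshold (75 ng/mL for apixaban, edoxaban and rivaroxaban"; the enoxaparin limit is 0.25 IU/mL. Section 11.5.3 states: "All efficacy analyses will be performed on the efficacy analysis population". Section 11.5 says the same for primary, secondary and exploratory endpoints.

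The adjudication committee's remit in Section 12.0 is wider than that population: "Adjudication of hemostatic efficacy, deaths, TEs, and post-surgical bleeding events for all patients".

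On blood loss, Section 10.4.2 has observed loss estimated in millilitres at the end of surgery, and adds: "Predicted blood loss must be determined by the investigator prior to the first incision". Table 3 (Section 11.5.1) brings blood loss, by its amount or its character, into the definition of Good. The assessment form attached to Administrative Change Letter #2 mentions amount only. Section 11.5.2.1 counts Excellent and Good as effective.

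**The concern.** A subgroup summary needs patients on both sides of the cut. Here the rule that defines the population has already removed the lower side, so the baseline-activity table would repeat the overall result for direct inhibitors beside blank columns. The question behind it, whether hemostasis differs between low and high circulating inhibitor activity, would go unanswered. That question matters in a single-arm study meant to inform dosing in a later randomised trial (Section 3.1).

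The blood-loss split has a different weakness. The groups are not empty, but the grouping variable is measured after treatment, at the moment the outcome is rated, and is one of the things the rater considers. A lower success rate in the high-loss half could then be misread as efficacy that varies between kinds of patient.

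**Working it through.** **1. The plan's own figures.** Inputs from Section 11.6: 100 enrolled, 20% attrition, 95% confidence interval, half width below 11%.

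- Evaluable: 100 × (1 − 0.20) = 80.
- Worst-case Wald half width: 1.96 × √(0.5 × 0.5 / 80) = 0.1096, or 10.96 points. The stated figure reproduces.

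**2. Baseline-activity groups, direct inhibitors.** Membership requires baseline x ≥ 75 ng/mL. The lower group at cut point c is {x ≥ 75} ∩ {x < c}.

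| Cut point c (ng/mL) | Lower group | Upper group |
|---|---|---|
| 30 | empty, n = 0 | all direct-inhibitor patients |
| 50 | empty, n = 0 | all direct-inhibitor patients |
| 75 | empty, n = 0 | all direct-inhibitor patients, apart from any value of exactly 75 |

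This needs no distributional assumption. Local-laboratory eligibility values do not rescue the table: Section 11.7.4 says they are documented but not formally analysed, and eligibility by that route requires more than 100 ng/mL.

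**3. Enoxaparin.** Entry is at 0.25 IU/mL. The listed cut points are in ng/mL, so these patients cannot be placed on either side.

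**4. How many patients a wider population could add.** Planned attrition is 100 − 80 = 20. Section 11.6 gives as reasons cancelled surgery, discontinuation, non-evaluability and low baseline activity, without a breakdown. The number of treated surgical patients below 75 ng/mL therefore lies between 0 and about 20 under the plan's own assumption.

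**5. Precision of usable splits.** Worst-case Wald half width if all 80 were available:

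- Halves, n = 40: 1.96 × √(0.25 / 40) = 0.155, or 15.5 points.
- Tertiles, n ≈ 27: 1.96 × √(0.25 / 27) = 0.189, or 18.9 points.

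Groups would be smaller once enoxaparin is set aside. Either split is descriptive only.

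**6. Blood-loss split, illustration.** Model: poor hemostasis and blood loss are jointly normal with correlation ρ, success is the same threshold for everyone (no true effect modification), and blood loss is cut at its median. Overall success is assumed to be 81.9%, the rate in the earlier bleeding study (Section 1.4.7), because the protocol states no expected rate. The value of ρ is assumed and shown as a range.

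| ρ | Success below median | Success above median | Gap (points) |
|---|---|---|---|
| 0 | 81.9% | 81.9% | 0 |
| 0.2 | 86.1% | 77.7% | 8.4 |
| 0.5 | 92.4% | 71.4% | 21.0 |
| 0.7 | 96.6% | 67.2% | 29.4 |

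Any link between loss and rating produces a gap with no variation in efficacy behind it. The size depends entirely on ρ, which the documents do not give.

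**The case against.** The strongest reply is that the cut points are only examples and that Section 11.9 defers detail to the SAP. That lowers the weight of the point but does not remove it. None of the three examples can work in the stated population, and filling the lower groups would mean departing from Sections 11.3.3, 11.5 and 11.5.3.

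Several stronger readings are tempting, and the documents do not support them:

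- A reader might infer that everyone in the population is at or above 75 ng/mL. Enoxaparin patients enter on a different scale.
- A reader might infer that many treated patients fall below 75 ng/mL. Section 11.6 gives no breakdown, and the entry rules in Section 3.1 are meant to select patients with high activity.
- A reader might treat low-activity patients as the trial's only internal reference, or as a control. They also receive andexanet. The note to Figure 2 puts the estimated non-effective level at 30 ng/mL, so those between 30 and 75 may still be anticoagulated. Section 11.5.2.3 also plans observed against predicted blood loss, another within-patient reference.

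On blood loss, the reply is partly right. Loss is named only under Good, with character as an alternative to amount in Table 3. Unexpected loss from surgical complications is excluded from the rating (Section 11.5.1). The form asks for a comparison with normal, non-anticoagulated hemostasis, not with a fixed volume. Section 11.9 only summarises and does not say whether the volume is observed or predicted. These points weaken the circularity. They do not remove it if observed loss is meant, which is the natural reading.

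**Conclusion.** The mismatch over baseline activity is a contradiction within the protocol. For direct inhibitors, 0 patients can fall below 30, 50 or 75 ng/mL in the stated population, and the cut points are undefined for enoxaparin. This follows from the text alone.

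The blood-loss point is smaller. That subgroup can be tabulated, but a difference between its halves cannot be read as inconsistent efficacy. It would go too far to call any such difference wholly an artefact: in the illustration the gap runs from 0 points at ρ = 0 to 29.4 at ρ = 0.7, all on assumed correlations. The point also rests on reading the volume as observed loss.

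Neither point touches the primary estimate, its confidence interval, or any secondary or safety result. Correction is worthwhile because it turns an uninformative planned table into an informative one.

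**What to change.** In Section 11.9, and in the SAP table shells if they follow it, choose one of two options for baseline anti-fXa activity:

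- State that this subgroup is summarised descriptively in all treated patients who underwent surgery and have an adjudicated hemostasis rating, keeping 30, 50 and 75 ng/mL for direct inhibitors. Call the low-activity patients a descriptive reference, not a control, and report their number.
- Keep the Efficacy Analysis Population and use cut points above 75 ng/mL, for example tertiles.

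Either way, handle enoxaparin separately in IU/mL.

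For blood loss, split on predicted loss recorded before incision, or keep observed loss and label the table descriptive only. Predicted loss has a drawback: the assessment form itself calls it subjective.

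The cost is a few words. Adjudication of hemostasis for all patients and the recording of predicted loss are already planned, so no new data collection is needed. The first option does add one stated exception to the rule on the efficacy population.
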